4.2.2 Secondary Outcome Measures

A secondary aim of the present study is to examine the effects of exenatide on the absorption of

The Effects of Exenatide, a GLP-1 Agonist, on Alcohol Self-Administration in Heavy Drinkers
Version 1.8 10.5.20

alcohol in a sample of heavy drinkers. It is hypothesized that areas under the breath alcohol concentration curves in heavy drinkers obtained during the first 40 minutes after ingestion of the priming drink of alcohol will be significantly lower in subjects when they receive exenatide as compared to when they are given sham injections. Another secondary goal of this study will be to determine whether blood glucose levels enter into the hypoglycemic range in any of the study subjects receiving the combination of alcohol and exenatide. It is hypothesized that the proportion of subjects with post-trial blood glucose levels in the hypoglycemic range will not differ significantly between the sham injection and exenatide treatment trials.

5 Study Design

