Risks of alcohol self-administration

There is a potential risk of increased alcohol consumption following the alcohol self-administration experiment, but studies of subjects who have completed the alcohol self-administration procedure indicate that this is rare. Social drinkers who completed an alcohol self-administration study were not found to have increased risk for problem drinking 6 weeks after completing the self-administration study⁶¹. Similar results were found for alcohol dependent subjects 3 months after participation in a study testing the effects of naltrexone on alcohol self-administration⁶². Young social adult drinkers also did not exhibit an increase in real life drinking 6 weeks after the completion of intravenous alcohol self-administration experiments⁶³.

Subjects may reach a level of intoxication that is uncomfortable to them. If a subject consumed all eight drinks that were available to them during the two one-hour alcohol Challenge Trials, there is a possibility that they could reach an estimated peak BAC of 0.09 to 0.13g/dl taking into account the rate of metabolism of 0.010 to 0.020 g/dl per hour⁶⁴. This risk is unlikely to be a problem because we are recruiting subjects who routinely engage in binge drinking and have likely developed some tolerance to alcohol. The alcohol self-administration paradigm that we have chosen does not include any coercion, inducements, or pressure to consume more alcohol than subjects feel comfortable consuming. There are no experimental manipulations that would increase drinking (e.g., heavy-drinking confederate, anxiety manipulation). In fact, in this study design there are inducements for subjects to not drink beyond the initial priming dose. Subjects will receive monetary incentives for each drink that they do not consume. To reduce the risk of injury or harm after the subject has been discharged from self-administration laboratory, we will require that subjects have a plan for transportation that does not involve the subject driving. Subjects must have a BAC below 0.04 g/dl prior to discharge from the alcohol self-administration trials.

Risk of loss of confidentiality

There is some risk that health information collected as part of this study could be seen by unauthorized individuals. Every effort will be made to minimize this risk and protect subject confidentiality.

Adequacy of Protection against Risks

A) Recruitment and Informed Consent

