The effects of the interaction of GLP-1 agonists and alcohol on blood glucose levels has not been adequately studied in humans. The administration of exenatide will decrease plasma glucagon in Type 2 diabetic patients and also may increase insulin release if blood glucose levels are elevated¹³. In fasting elderly Type 2 diabetic patients receiving the antidiabetic sulfonylurea glyburide, alcohol ingestion produced a greater decrease in blood glucose levels than did placebo⁶⁵. Also, ethanol has also been shown to inhibit gluconeogenesis in Type 2 diabetes, although it did not produce alterations in total liver glucose output¹². The consumption of alcohol in healthy subjects receiving the sulfonylurea glipizide did not result in a greater reduction in glucose blood levels than when this drug was taken alone, but did prolong the length of time during these reductions occurred⁶⁶. As a precaution against subjects experiencing hypoglycemia in this study, alcoholic drinks will be administered to subjects with a sugary mixer (e.g. juice, soda). As a protection for the risk of allergic reaction, injections will be performed in the GCRU.

Risks of Phlebotomy

To minimize the risk of pain, bruising, lightheadedness, fainting, and on rare occasions, infection from a blood draw, we will use trained phlebotomists.

Risks of alcohol self-administration

To minimize the risk of subjects reaching a level of intoxication that is uncomfortable to them,

The Effects of Exenatide, a GLP-1 Agonist, on Alcohol Self-Administration in Heavy Drinkers
Version 1.8 10.5.20

we will remind subjects that they can discontinue study participation at any time. Subjects will be monitored during the course of the study, both through direct assessment with study staff and by observation through a video camera in the alcohol laboratory. Medical staff will evaluate subjects and may make a determination to halt study participation if the subject becomes too behaviorally impaired or if there are emergent safety issues. Subjects who have a BAC greater than 0.04 g/dl or who appear to be too behaviorally impaired to leave our research center will be asked to remain in the clinic until their intoxication is reduced to a level that it is safe to discharge them from the research laboratory.

Risk of loss of confidentiality

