Subjects will be given a priming drink designed to increase the subject's blood alcohol level (BAL) to 0.03g/dl, using the alcohol of their choice that is 24% Alcohol By Volume (ABV) or greater. Drinks will be mixed with a sugary mixer (3:1 Mixer:Alcohol) to preclude the occurrence of hypoglycemia. The volume of alcohol will be calculated using an online tool developed by UW-Madison (<http://dionysus.psych.wisc.edu/WebCMS/baccalc.htm>) based on a formula described by Watson⁵¹. The subjects will be asked to drink the priming drink over a period of 5 minutes. The purpose of the priming drink is to normalize drinking in the laboratory.

Absorption period. Subjects will be observed for 40 minutes following the priming dose of alcohol. This period will provide ample time for subjects to reach the target BAC. Breathalyzer readings will be completed at 10 minutes intervals.

Alcohol self-administration Blocks 1 and 2. In each of the alcohol self-administration Blocks, subjects will be presented with four drinks, each mixed to raise their BAC by 0.0125g/dl. They will be told that they can either consume the desired number of drinks over the following 60 minutes, or they will receive the equivalent dollar amount of the cost of each drink (\$3.00) they did not consume. At the end of each 1-hour session the drinks will be removed and the volume of alcohol remaining will be measured with a graduated cylinder. Cravings will be assessed using the AUQ and VAS every 30 min during the self-administration blocks. BAC levels will be obtained at the end of the Block 2 session as will blood glucose levels. Blood glucose levels will be measured at the end of Block 2 using a glucometer and blood obtained from a pinprick sample. If the subject is found to be hypoglycemic (glucose < 70 mg/dL), staff will give the subject orange juice and re-test in 30 minutes. If the subject is found to be hyperglycemic (glucose > 300 mg/dl), staff will escort the subject to the BMC emergency department for evaluation. At the end of this session subjects will also be asked to rate their experience of nausea using a visual analog scale developed to assess nausea in an emergency department⁵². Subjects will be assessed for safety prior to subjects leaving the laboratory. Subjects will not be released until their BAC is below 0.04 g/dl and they are not behaviorally impaired.

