10.4 Stopping Rules

There are no interim analyses planned that would allow for a determination of futility or overwhelming benefit. Study enrollment will be suspended under the following circumstances:

1. Serious Adverse Events. Study enrollment will be suspended in the event of a single serious adverse event that is determined to be unexpected and at least possibly related. If suspended, study recruitment will not continue until a determination has been made about whether the known risks of participation have changed and the BU Medical Campus/Boston Medical

Center IRB has made a finding that the risk/benefit ratio remains favorable given the possible newly identified risk.

2. Risk of intoxication. Subject recruitment will also be suspended if more than one subject of the first ten subjects enrolled is discontinued by the investigator due to intoxication during the alcohol self administration trial. Due to differences in alcohol tolerance, BAL is not a reliable measure of subjects potentially posing a safety risk. Study staff will make a subjective determination of risk based on the subject's behavior. After 10 subjects have been enrolled, the trial will be suspended if there are more than 10% of subjects whose participation has been halted by the study team due to concerns about physical safety because of intoxication during the alcohol self-administration trial. If suspended for this reason, the study team will consider design changes to reduce the likelihood of this as a potential risk to study subjects. Recruitment would resume when the BU Medical Campus/Boston Medical Center IRB has made a determination that proposed changes to the study design have an acceptable risk/benefit ratio.

11 Data Handling and Record Keeping

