2. Subjects will report lower levels of craving as measured by the Visual Analog Scale (VAS) and the Alcohol Urge questionnaire (AUQ) during the exenatide Challenge Trial compared to the sham injection Challenge Trial.	Craving measures (AUQ and VAS) collected at 30-minute intervals during the self-administration trials will be used to test the effect of exenatide on alcohol craving. A mixed models approach will be used to test for differences in craving between the exenatide and sham injection Challenge Trials. Within-subject factors for this analysis will include Treatment and Time Block. Trial order will be used as covariate in these analyses to allow evaluation as to whether the order of treatments has a significant effect on the outcome.
Hypothesis 3: Areas under the breath alcohol concentration curves (AUC's) in heavy drinkers obtained during the first 40 minutes after ingestion of the priming drink of alcohol will be significantly lower in subjects when they receive exenatide as compared to when they are given sham injections	AUC's for BAC obtained using data obtained during the 40-minute absorption period will be compared between Challenge Trials using a repeated measures mixed models approach. In addition, individual BAC values obtained at 10-minute intervals after alcohol ingestion of the priming drink also will be compared between the sham injection and exenatide treatment trials using a repeated measures mixed models approach. A significant time x trial interaction value also will be taken to indicate a significant between trial difference in the rates of alcohol absorption.
Hypothesis 4. The proportion of subjects with post-trial blood glucose levels in the hypoglycemic range will not differ significantly between the sham injection and exenatide trials.	The proportion of subjects with blood glucose values below 50 mg/dl will be compared within subjects using the McNemar's test. We hypothesize that there will be no difference in blood glucose levels between the alcohol Challenge Trials.

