	Baseline (May be split over 2 visits)	Randomization & Trial1	Trial 2
Clinic Visit #	0	1	2
COVID-19 Screening Questionnaire (pre-visit)	X	X	X
Informed Consent	X		
Urine Drug Screen ^A	X	X	X
Locator Form	X		
Demographics	X		
Medical History	X		
Physical Exam	X		
MINI V 6.0	X		
CBC w Diff AST, ALT, GGT, Tbili, BUN, Ca, CO2, Cl, Cr, G K, Na, Triglycerides, Serum lipase, Ha1c	X		
Vital Signs, weight, Blood Alcohol Level ^{b, c}	X	X	X
ECG	X		
Prior and Concomitant Meds	X	X	X
CIWA-AR	X	X	X
Eligibility Checklist		X	
Confirm Eligibility to continue		X	X
Urine Pregnancy Test	X	X	X
Birth control assessment	X	X	X
AEs	X	X	X
C-SSRS	X	X	X
Treatment Referral			X
TLFB (28 day at baseline)	X	X	X
Alcohol Craving VAS ^c		X	X
OCDS ^c	X	X	X
AUQ ^c		X	X
Nausea VAS		X	X

The Effects of Exenatide, a GLP-1 Agonist, on Alcohol Self-Administration in Heavy Drinkers
Version 1.8 10.5.20

	Baseline (May be split over 2 visits)	Randomization & Trial1	Trial 2
Clinic Visit #	0	1	2
Blood Glucose (at end of block2)		X	X

A) Test for opioids, cocaine, amphetamines, methamphetamine, tetrahydrocannabinol (THC), barbiturates, oxycodone, buprenorphine, methadone and benzodiazepines, and alcohol (Ethyl Glucuronide)
B) if the baseline visit is split between two days, vitals, breathalyzer, and weight are to be taken at each visit.
c) See Table 2 for specific administration times

Items highlighted in blue will be performed in-clinic remote. The study staff and subject will connect through video call while located in separate rooms in the Clinical Studies Unit to avoid unnecessary face-to-face contact. Forms that must be filled out by the subject will be left on a clipboard in the exam room to be occupied by the subject, and study staff will instruct subjects to fill out the forms. Forms filled out by study staff through interviewing the subject will be kept in the study staff's room. The COVID-19 screening questionnaire will be administered before the subject arrives for their in-clinic visit.

Items highlighted in yellow will be performed with social distancing. The study staff and subject will be located in the same room, but will maintain a 6-foot distance and both persons will wear PPE at all times.

Items highlighted in green require direct contact between study staff and subject. Contact will be limited to minimum necessary and PPE will be worn at all times by both study staff and subject.

The Effects of Exenatide, a GLP-1 Agonist, on Alcohol Self-Administration in Heavy Drinkers

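### Trial-day glucose is scheduled only at the end of Block 2, so a session that ends early has no scheduled reading for the hypoglycemia aim

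*Combined protocol and SAP*

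**What the plan says.** **When glucose is measured.** Section 9 (self-administration Blocks 1 and 2): "Blood glucose levels will be measured at the end of Block 2 using a glucometer and blood obtained from a pinprick sample". The Appendix A row reads "Blood Glucose (at end of block2", for Trials 1 and 2. Appendix B, the drinking-lab schedule, has no glucose row. The only other trial-day reading is the 30-minute re-test that follows a value below 70 mg/dL.

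**When a session can end earlier.** Under Section 6.1, "we will remind subjects that they can discontinue study participation at any time", and medical staff "may make a determination to halt study participation if the subject becomes too behaviorally impaired or if there are emergent safety issues". Section 10.4 also provides for halts because of intoxication, judged from behavior, since it regards blood alcohol level as an unreliable guide to risk. Neither section mentions glucose at an early stop. Section 9 requires a safety assessment before a subject leaves but does not name glucose as part of it.

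**What the reading is for.** The secondary aim in 4.2.2 is to "determine whether blood glucose levels enter into the hypoglycemic range in any of the study subjects receiving the combination of alcohol and exenatide". For Hypothesis 4, Section 12.1 states: "The proportion of subjects with blood glucose values below 50 mg/dl will be compared within subjects using the McNemar's test". The predicted result is no difference. Section 11.3 requires missing data to be explained on the case report form. No section says how a missing glucose value is treated in the analysis.

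**The concern.** The aim in 4.2.2 concerns whether hypoglycemia occurs in any subject, so a handful of unmeasured sessions matters more than it would for a comparison of means. Section 6.1 itself says that the joint effect of GLP-1 agonists and alcohol on glucose has not been adequately studied in humans.

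The unmeasured sessions may also not be a random subset. Impairment is a named reason for a halt, and low glucose could contribute to impairment. That link is an inference; the documents do not state it. Without a reading, though, the two causes cannot be told apart afterwards.

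For Hypothesis 4, McNemar's test uses only subjects with a value in both trials. One unmeasured session therefore removes the subject, and any lost exenatide-only event moves the result toward the predicted absence of a difference.

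**Working it through.** **1. The plan's own figures.** Section 12.2 gives 28 completers for alcohol consumption (effect size 0.7, alpha 0.01, power 0.81). An exact two-sided paired t-test with n = 28 gives power 0.815, so this reproduces. It has no bearing on glucose, for which no sample size, power or alpha is stated.

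**2. Timing (Section 9 and Figure 2).** Counting from injection, with the full 30 minutes before the priming drink:
- Block 1 starts at 30 + 5 + 40 = 75 minutes.
- Block 1 ends at 75 + 60 = 135 minutes.
- Block 2 ends at 135 + 60 = 195 minutes.

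Section 9 puts peak exenatide at about 90 to 120 minutes, which falls inside Block 1. A session that stops then ends near peak exposure, and its next scheduled glucose time would have been 60 to 120 minutes later (195 − 135 to 195 − 75).

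**3. How many sessions.** No rate of early ending is given. The only bound is in 10.4: after the first ten subjects, "the trial will be suspended if there are more than 10% of subjects whose participation has been halted by the study team" for intoxication. Taking the 36 randomized as denominator (an assumption), 0.10 × 36 = 3.6, so at most 3 halts. With 28, 0.10 × 28 = 2.8, so at most 2. Voluntary withdrawals and halts for other safety reasons fall outside this bound.

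**4. Effect on the McNemar result.** Alpha 0.05 is assumed. With k discordant pairs all in one direction, exact two-sided p = 2 × 0.5^k: k = 3 gives 0.25, k = 4 gives 0.125, k = 5 gives 0.0625, k = 6 gives 0.031. Six are needed. Suppose 36 pairs and 6 exenatide-only events, with some of those subjects unmeasured:

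| Event pairs lost | Observed | p |
|---|---|---|
| 0 | 6/36 = 16.7% | 0.031 |
| 1 | 5/35 = 14.3% | 0.063 |
| 2 | 4/34 = 11.8% | 0.125 |
| 3 | 3/33 = 9.1% | 0.25 |

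The loss changes significance only if true events are already this common.

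**5. The test is weak anyway.** With a true exenatide-only rate of 10% and no sham-only events, power = P(X ≥ 6), X ~ Binomial(n, 0.10): 0.145 at n = 36, 0.106 at 33 and 0.055 at 28.

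**6. Effect on the descriptive aim.** With no events seen, the one-sided 95% upper bound is 1 − 0.05^(1/n): 8.0% at n = 36, 8.7% at 33 and 10.1% at 28. Fewer readings widen the bound only slightly. The larger risk is an event that is never measured. As a labelled worst case, if 3 subjects were halted, all 3 were hypoglycemic and the other 28 were not, the study would report 0/28 where the truth was 3/31 = 9.7%. Even fully measured, three one-way pairs give p = 0.25.

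**The case against.** **A reader might infer that early endings are common and often due to impairment.** The documents do not support this. Impairment is one named reason, no frequency is given, and Section 6.1 says of intoxication: "This risk is unlikely to be a problem because we are recruiting subjects who routinely engage in binge drinking". This objection stands.

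**A reader might infer that such subjects will have no glucose value at all.** The plan is silent; it does not forbid a reading. Section 6.1 keeps anyone above 0.04 g/dl or too impaired in the clinic, so staff could take one. A subject who merely stops drinking but stays to the end of Block 2 is measured as planned. This also stands: the accurate statement is that there is no scheduled value. But an optional reading at an unspecified time, with no rule for its use, does not define an endpoint.

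**A reader might infer that a low glucose would be counted under the wrong suspension rule in 10.4.** That section has no hypoglycemia rule to confuse it with, and a halt counted as intoxication moves the study toward suspension, which is the cautious direction.

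**Low glucose may be rare here.** Drinks carry a 3:1 sugary mixer, a history of diabetes is excluded, and Section 6.1 cites no increase in hypoglycemia with GLP-1 in fasting healthy subjects. This lowers the expected count, but 4.2.2 still sets out to check.

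**An early reading cannot rescue every pair, and it mixes treatment with time.** A subject discontinued in Trial 1 has no Trial 2 value whenever glucose is taken. Pairing a Block 1 reading with one at about 195 minutes compares different times after injection. Both points stand and limit what the change can do for McNemar's test.

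**Conclusion.** The gap is real and worth closing: followed as written, the plan schedules no glucose reading for a session that ends before the end of Block 2, and the aim in 4.2.2 is the part that suffers. The number of sessions is unknown. The 10.4 rule caps intoxication halts at about 3 of 36 before suspension, and that cap excludes withdrawals and other safety halts.

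The documents do not show that the Hypothesis 4 conclusion would change. That would need at least six one-way events, some of them unmeasured, under an assumed alpha of 0.05, and the test has little power in any case. That lost sessions would be enriched for low glucose is plausible but rests on inference. The case for change lies in the descriptive safety aim and the low cost of meeting it.

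**What to change.** 1. In Section 9 and both appendices, schedule the glucose reading at the end of Block 2 or when the subject's session ends early, whichever is first. Define an early end as being halted or leaving, not as declining further drinks. Record the clock time, the time since injection and the reason.
2. Add to Section 12.1 a descriptive report of hypoglycemia by treatment among all subjects dosed, including those with no second trial, counting every such value and stating how many sessions have none.
3. Keep McNemar's test on pairs. Flag early readings, run the test with and without them, and report missing pairs by treatment and reason.
4. Reconcile the two hypoglycemia thresholds: Section 9 uses below 70 mg/dL and Section 12.1 uses below 50 mg/dl.

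What is done in response to a value stays with the existing text. Breath alcohol and the craving scales need no change here, because Appendix B already has them every 30 minutes during the blocks. The cost is the same pinprick taken earlier in a few sessions, some readings at a different time after injection, and a short addition to the analysis text.

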10.1 Definitions

The following definitions will be used in the assessment of safety:

Adverse Event (AE) is any untoward or unfavorable medical occurrence in a human subject, including any abnormal sign (for example, abnormal physical exam or laboratory finding), symptom, or disease, temporally associated with the subject's participation in the research, whether or not considered related to the subject's participation in the research.

Serious Adverse Event (SAE) is any adverse event that

- (1) results in death;
- (2) is life-threatening;
- (3) results in inpatient hospitalization or prolongation of existing hospitalization;
- (4) results in a persistent or significant disability/incapacity;
- (5) results in a congenital anomaly/birth defect; or
- (6) based upon appropriate medical judgment, may jeopardize the subject's health and may require medical or surgical intervention to prevent one of the other outcomes listed in this definition (examples of such events include allergic bronchospasm requiring intensive treatment in the emergency room or at home, blood dyscrasias or convulsions that do not result in inpatient hospitalization, or the development of drug dependency or drug abuse).

Life-threatening means that the event places the subject at immediate risk of death from the event as it occurred.

Unanticipated Problem is defined as an event, experience or outcome that meets **all three** of the following criteria:

- is unexpected; AND
- is related or possibly related to participation in the research; AND
- suggests that the research places subjects or others at a greater risk of harm (including physical, psychological, economic, or social harm) than was previously known or recognized.

Possibly related means there is a reasonable possibility that the incident, experience, or outcome may have been caused by the procedures involved in the research

Unexpected means the nature, severity, or frequency of the event is not consistent with either:

The Effects of Exenatide, a GLP-1 Agonist, on Alcohol Self-Administration in Heavy Drinkers
Version 1.8 10.5.20

- the known or foreseeable risk of adverse events associated with the procedures involved in the research that are described in (a) the protocol-related documents, such as the IRB-approved research protocol, any applicable investigator brochure, and the current IRB-approved informed consent document, and (b) other relevant sources of information, such as product labeling and package inserts; or
- the expected natural progression of any underlying disease, disorder, or condition of the subject(s) experiencing the adverse event and the subject's predisposing risk factor profile for the adverse event.

